6.1. Study population

Between March 30th, 2014 and December 31th, 2017, we recruited a large cohort of 268 PD patients within the frame of the "Amyloid-Beta in cerebrospinal fluid as a risk factor for cognitive dysfunction in Parkinson's Disease" (ABC-PD, ethic protocol 686/2013B01) study. Follow-up visits were conducted between July 2018 and September 2020, all patients of the ABC-PD study were contacted for re-examination.

We propose a second follow-up of the already existing longitudinal cohort described above with a longitudinal assessment including neuropsychological in-depth endophenotyping and CSF biomarker analyses. In total 182 patients will be invited to participate in the second

follow-up assessment. If patients are not able to attend a clinical visit in-house, possibility of assessments at patients' homes shall be offered. Moreover, if patients are not able to give consent for study participation (confirmed by an independent physician), the legal guardian will be contacted to give study consent for participation. Legal guardians are defined as persons with legal care directive or lasting power of attorney. For drop-outs different reasons for drop-out will be coded (e.g. deceased, disabled, disinterested/refuse study participation, unable to reach/unknown address).

Diagnosis of cognitive impairment:

Patients were classified as PD-MCI according to Level-II Movement Disorder Society recommendations if cognitive impairment was present but did not significantly interfere with everyday function [25]. PDD was defined according to Movement Disorder Society Task Force criteria [17] if cognitive impairment was present and severe enough to impair ADL function unrelated to motor or autonomic symptoms and at least one behavioral symptom was present to support diagnosis. Cognitive impairment was defined according to Level-I (impairment of global cognition) for patients with minimal assessments, or Level-II (performance below 1.5 standard deviation of the population mean reported in the test manuals on at least two tests) for patients assessed using a full cognitive battery. Patients not meeting either of the diagnostic criteria were classified as PD-CN. Cognitive status at follow-up was defined as the primary study outcome.

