6.3. Recruitment

Participants of the already recruited ABC-PD cross-sectional cohort (ethic protocol: 284/2018BO1) will be asked to participate in the follow-up assessment. Patients who did not agree to participate in a longitudinal study or who have asked not to be contacted after the first cross-sectional assessment will not be contacted again. A drop-out rate of 20% is expected for follow-up retention. Therefore, investigation of 145 patients will be primarily conducted between January 2023 and June 2024. During the executive project phase, around 7 to 9 patients will be assessed per month. Patients will be contacted either via phone or in written form. Reasons for drop-outs will be registered for data analysis.

7. Statistics and Sample size estimation

All following hypotheses will be tested a priori; no post-hoc corrections of p-values will be conducted.

Characterization of study groups: Between-group comparisons at clinical visits will be conducted using Mann-Whitney-U or Welch test (two groups) or Jonckheere-Terpstra test (>2 groups) for numerical variables and χ^2 test or Exact Fisher Test for categorical variables. Post-hoc comparisons for IADL and cognitive variables between groups will be corrected for between-group covariates via linear regression models with group status as dummy coded variable. When follow-up cognitive groups are compared (PD-CN vs. PD-MCI vs. PDD), analyses with covariates will be run twice with reference category set as either PD-CN or PD-MCI.

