Prediction of cognitive progression along with progression in ADL function over time: In patients who completed all visits, the predictive values of baseline/follow-up IADL (patients' self-impression vs. informant-rating), stratification (cognitive IADL impairment vs. motor IADL impairment), cognitive status (PD-CN vs. PD-MCI), and both markers combined (PD-MCI + cognitive IADL impairment) will be calculated using multivariate Cox Proportional-Hazard models. Akaike's information criterion (AIC) and concordance index (C-index) [26] will be used as model fit indices. Logistic regression with follow-up cognitive diagnosis (PD-CN vs. PD-MCI or non-demented vs. PDD) as dependent variable will evaluate whether baseline status of cognitive IADL impairment (FAQ quotient >1.008) predicted risk of PDD conversion independent of other clinical variables (e.g., cognitive status), biomarker profile, and covariates. As a post-hoc exploratory analysis to identify which subscore best predicted PDD conversion, ROC curves will be calculated for all FAQ scores (self- and caregiver-assessment). The optimal score/cut-off will be chosen according to the highest Youden Index. Linear regression will be applied to investigate predictors of neuropsychological scores and IADL measures at follow-up(s).

2. Defining the interaction of progression in markers over time

Generalized linear mixed effects models (GLMMs) will evaluate progression in neuropsychological tests and IADL scores over time. Correlation analyses are planned to investigate association in change of scores over time of different measures.

Sample size calculation:

Between the baseline and first follow-up 17 (10.4%) patients developed PDD within a mean follow-up interval of 3.78 ± 0.84 years (range: 1.67-5.79 years), with higher rates of converters in patients with baseline status of cognitive ADL impairment (29.7%). Estimated follow-up interval between first and second follow-up are expected to be very similar, and a higher rate of patients with cognitive ADL impairment were identified. Moreover, the risk for PDD development is increased in later disease stages [27, 28]. Therefore, a maximum of additional 15 converters are expected.

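### The exploratory search for the best FAQ score and cut-off has no optimism correction, so the accuracy it reports will be too favourable

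*Combined protocol and SAP*

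**What the plan says.** The step is in Section 7 (Statistics and Sample size estimation), in the paragraph on prediction of cognitive progression. It is introduced with "As a post-hoc exploratory analysis to identify which subscore best predicted PDD conversion". The plan continues: "ROC curves will be calculated for all FAQ scores (self- and caregiver-assessment"), and the selection rule is "The optimal score/cut-off will be chosen according to the highest Youden Index".

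On event numbers, the sample size paragraph of the same section reports "Between the baseline and first follow-up 17 (10.4%) patients developed PDD", and for the coming interval "Therefore, a maximum of additional 15 converters are expected". On patient numbers, Section 6.1 says "In total 182 patients will be invited to participate in the second" follow-up, and Section 6.3 says "A drop-out rate of 20% is expected for follow-up retention" and "Therefore, investigation of 145 patients will be primarily conducted between January 2023 and June 2024".

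The protocol names no hold-out sample, cross-validation, bootstrap correction or external cohort for the selected score, and no confidence interval for the selected cut-off. It does not say whether the ROC step uses only the new converters or pools them with the earlier ones.

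**The concern.** The rule takes a maximum twice: over every threshold of a score, and over every score and rater. The highest observed sum of sensitivity and specificity is partly real discrimination and partly the luck of that sample. With few converters the luck is a large part. Sensitivity suffers most, because with 15 converters each one is worth about 7 percentage points (1/15 = 6.7%).

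Two results are at stake. One is the accuracy quoted for the new cut-off. The other is which subscore, from which rater, is named best.

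This study has a precedent for such results travelling. Section 3.2 describes a post-hoc ROC analysis with 17 converters that yielded the FAQ quotient cut-off of 1.008. Section 4.1 now uses that value in the main hypothesis, and Section 7 uses it as the logistic-regression predictor.

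**Working it through.** **1. The plan's own figures.** Converters so far: 17/164 = 10.4%, as stated. Expected sample: 182 × (1 − 0.20) = 145.6, against the stated 145. Both reproduce. Converters available to the ROC step: at most 15 new, or 17 + 15 = 32 if pooled. The plan states no target precision or expected accuracy for this step, so there is no planned figure to reproduce for the ROC analysis itself.

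**2. A reference point from the documents.** At the earlier cut-off (quotient > 1), 37 patients were classified as impaired and 29.7% converted: 0.297 × 37 = 11. Sensitivity is 11/17 = 65% (exact 95% CI 38 to 86%). Specificity is (147 − 26)/147 = 121/147 = 82%. The Youden Index is 0.65 + 0.82 − 1 = 0.47. Even before any search, sensitivity is known only to within about 25 points either way.

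**3. Assumptions for the simulation (not in the documents).**
- Number of scores: Section 3.2 names total, motor and quotient scores, and a cognitive score is implied. Four scores from two raters give 8; the range tried is 1 to 8.
- Correlation between scores: 0.5 to 0.8.
- True AUC: 0.5 to 0.8.
- Sample: 15 or 32 converters among 145, or 17 among 164. Taking 32 of 145 is a simplification, since not every earlier converter will return.
- Scores are binormal, with 1,500 runs per setting.

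In each run the score and cut-off with the highest apparent J = sensitivity + specificity − 1 are chosen. Apparent J is compared with the true J of that same choice, Φ(d − c) + Φ(c) − 1, where c is the cut-off and d = √2 · Φ⁻¹(AUC).

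**4. Mean overstatement (apparent minus true J).**

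| Setting | 15 converters | 32 converters |
|---|---|---|
| 8 equal scores, continuous | 0.20 to 0.26 | 0.14 to 0.20 |
| 8 equal scores, coarse (AUC 0.6 to 0.8) | 0.17 to 0.19 | 0.12 to 0.14 |
| 8 unequal scores (one AUC 0.8, the rest 0.6 to 0.7) | 0.16 | 0.10 |
| 1 score (cut-off search only) | 0.12 to 0.16 | 0.08 to 0.12 |

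With 17 of 164, eight equal continuous scores give 0.19 to 0.25.

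**5. Examples.**
- Eight scores, AUC 0.7, correlation 0.8, 15 of 145: apparent J 0.48 against true 0.27. Sensitivity is reported as 78% against a true 60%; specificity as 70% against 67%.
- Eight scores with no predictive value (AUC 0.5), 15 of 145: apparent J still averages 0.24 to 0.26, with a true value of 0.

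**6. Stability of the choice.** One score with true AUC 0.75 against seven at 0.70 (correlation 0.65) is selected in about 35% of runs with 15 converters and about 45% with 32. Picking at random would give 1/8 = 12.5%.

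**7. What bootstrap correction achieves.** Here the assumed AUCs are 0.60 to 0.82, with correlation 0.65 and the full selection repeated in each resample (200 data sets, 100 resamples each). Mean J:

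| Sample | Apparent | Corrected | True | Share of bias removed |
|---|---|---|---|---|
| 15 of 145 | 0.583 | 0.471 | 0.418 | 0.112/0.165 = 68% |
| 17 of 164 | 0.574 | 0.473 | 0.422 | 0.101/0.152 = 66% |
| 32 of 145 | 0.543 | 0.465 | 0.442 | 0.078/0.101 = 77% |

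**The case against.** The strongest reply is that the plan labels the step exploratory. It is neither the main hypothesis, which fixes the cut-off at 1.008, nor the main Cox and logistic models. This stands as a limit on how much the step can be asked to prove, and it keeps the point from being more serious. It does not make the reported accuracy less biased, and the history of 1.008 shows that the label does not stop a result from being carried forward.

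Several stronger readings are tempting, and the documents do not support them.

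- *That this step decides whether patient or informant ratings predict better.* Section 7 gives that comparison first to the Cox models, with AIC and C-index. The ROC step includes both raters, but its stated purpose is to compare subscores. It is a secondary source for the rater question.
- *That the new cut-off will be used to select trial populations.* Section 3.1 only suggests that patients with PD-MCI and cognitive IADL impairment may be a useful target group, and adds that confirmation is needed. It refers to the existing classification, not to a cut-off still to be chosen.
- *That the winning score is largely chance.* This needs eight equally good scores. Section 3.2 points the other way: the quotient did best and the motor score had an AUC of only 0.60. With assumed AUCs of 0.60 to 0.82, the truly best of eight scores was selected in 48% of runs with 15 events and 58% with 32, and the motor scores never. The choice is noisy, not random.
- *That the plan prescribes reading accuracy from the same patients.* It does not say so. This is inferred because no other data or correction is named.

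It is also fair that FAQ items are integers from 0 to 3 and that pooling could give 32 events. Both reduce the bias, as the table shows, but neither removes it.

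**Conclusion.** The point holds as a weakness in an exploratory analysis that should be corrected. Following the stated rule gives an optimistic Youden Index, by roughly 0.10 to 0.26 for eight candidate scores. The upper end belongs to 15 converters and continuous scores, the lower end to 32 converters with coarse or clearly unequal scores. The direction was the same in every setting tried. The size rests on the number of scores, their correlation and their true AUCs, none of which the documents give.

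The point concerns only the score and cut-off newly selected here. It says nothing against testing the pre-fixed 1.008 in the new converters, provided they are analysed apart from the 17 from whom it was derived.

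**What to change.** Keep the step exploratory and add to Section 7:

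- The whole selection, across all FAQ scores, both raters and all thresholds, is repeated inside each bootstrap resample.
- Optimism-corrected Youden Index, sensitivity and specificity are reported beside the apparent values.
- The report gives how often each score and rater is selected, and a bootstrap interval for the cut-off.
- The chosen score and cut-off are described as unvalidated, because the correction removes most of the bias but not all of it.
- No best rater or subscore is named from apparent values alone.
- The text states which converters enter the step: the new ones only, or pooled with the earlier 17.

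The cost is a little more analysis code and a less favourable reported accuracy. No new data, patients or visits are needed.

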3.2. Preliminary data

Methods. The study was conducted as the first follow-up (Title: Cognitive driven ADL impairment as a predictor for PDD; ethic protocol: 284/2018BO1) of "Amyloid-Beta in Cerebrospinal Fluid as a Risk Factor for Cognitive Dysfunction in Parkinson's Disease" (ABC-PD) study (ethic protocol: 686/2013BO1).

The FAQ quotient (cut-off >1), indicating more cognitive than motor-driven IADL impairment, defined cognitive IADL impairment status at baseline ($FAQ_{Q>1}$). The FAQ is a ten item IADL assessment scored on a 4-point Likert scale ranging from normal (score=0) to dependent (score=3) ADL function (max. points 30) [23]. The FAQ quotient was developed by differentiating cognitive and motor aspects of the individual items. Ten linear regressions were conducted defining each FAQ item as the dependent variable, and the Unified Parkinson's Disease Rating Scale Part III (UPDRS-III, motor assessment) as well as the Montreal Cognitive Assessment (MoCA) total score as independent variables, with age, sex, and disease duration entered as covariates [24]. Hazards ratios (HR) were used to compare the impact of different baseline classifications on dementia conversion.

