Results. Of 268 patients with PD assessed at baseline, 108 (40.3%) had PD-MCI. After a period of 3.8 ± 0.8 years, 182 (61.2%) patients were re-assessed and 164 analysed (17 excluded due to deep brain stimulation, one patients without classification of cognitive group). At follow-up, 93 (56.7%) patients fulfilled criteria for normal cognitive function (PD-CN), 54 for PD-MCI (32.9%), and 17 (10.4%) had developed dementia. Predictive ratio of baseline cognitive IADL impairment (n=37; 21.3%) for dementia conversion was descriptively higher than for PD-MCI, but highest in patients with both markers [HR=12.01, 95%-confidence interval (CI): 4.47-32.23]. Nearly half of patients (n=10, 47.6%) with baseline classification of cognitive IADL impairment and PD-MCI converted to dementia. Baseline status of cognitive IADL impairment was associated with higher non-motor burden, worse cognitive performance, and more severe IADL progression over the study period. In a post-hoc Receiver Operating Characteristic (ROC) analysis, the FAQ quotient (cut-off >1.008) was confirmed to best predict conversion to dementia compared to other IADL scores. Only two patients with baseline status of cognitive IADL impairment in our sample scored below the newly identified FAQ quotient cut-off of 1.008 resulting in a total of 35 (21.3%) patients with values above this defined cut-off. The FAQ motor score [AUC(area under the curve)=0.60, 95%-CI: 0.52-0.67, $p=0.13$], reflecting predominantly motor aspects on IADL function, was not associated with PDD conversion.

4. Objectives of the study

Based on previous analyses in the sample we suggest that monitoring of both cognition and cognitive ADL impairment reflect neurodegeneration associated to PDD development. This study evaluates markers predicting cognitive and ADL long-term outcome in our sample. Additionally, we will investigate whether ratings of patients or informants best predicted decline of cognitive impairment and/or everyday function. Clinical data along with other clinical marker and biomarker status will be investigated.

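### Section 7 makes no allowance for unequal variances in the linear models for FAQ and other IADL scores; their standard errors would be too small if the smaller group is the more variable one

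*Combined protocol and SAP*

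**What the plan says.** Two parts of Section 7 apply linear regression to IADL scores.

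- **Prediction of progression.** "Linear regression will be applied to investigate predictors of neuropsychological scores and IADL measures at follow-up(s". This is the named method for predictors of IADL scores and so serves Aim 1.3 in Section 4.1, which concerns worsening on the ADL scales.
- **Characterization of study groups.** Comparisons of IADL and cognitive variables are to be "corrected for between-group covariates via linear regression models with group status as dummy coded variable". For the three cognitive groups, the model is run with PD-CN and then with PD-MCI as reference.

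The unadjusted comparisons in that second paragraph use "Mann-Whitney-U or Welch test (two groups) or Jonckheere-Terpstra test (>2 groups) for numerical variables". The Welch test is built for unequal variances.

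Section 3.2 describes the FAQ as a "ten item IADL assessment scored on a 4-point Likert scale ranging from normal (score=0) to dependent (score=3) ADL function (max. points 30" in total, so the best possible result lies on the lower bound. Neither part of Section 7 gives a standard-error estimator, transformation, residual check or ordinal model for these outcomes.

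**The concern.** An ordinary linear model with a group dummy pools the residual variance over the groups, and the larger group dominates the pooled value. If the smaller group is the more variable one, the pooled value understates the uncertainty of its mean. The standard error of the group difference is then too small.

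Both conditions are plausible here. The group with cognitive IADL impairment was about 21% of those analysed, and the PDD group was smaller still. On a scale with its floor at normal function, a higher mean usually brings a larger spread. The plan avoids the equal-variance assumption in the unadjusted two-group tests but returns to it once covariates enter. At stake is the stated certainty of the Aim 1.3 results and of the adjusted IADL group differences. Section 7 also rules out p-value corrections, so nothing else in the plan offsets an optimistic standard error.

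**Working it through.** **Inputs from the documents**

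- Planned N: 182 invited less 20% drop-out (Sections 6.1 and 6.3). 182 × 0.80 = 145.6, which agrees with the stated 145.
- Impaired share: "resulting in a total of 35 (21.3%) patients with values above this defined cut-off" (Section 3.2). 35/164 = 21.3%, and 0.213 × 145 ≈ 31, leaving 114. Section 3.2 also prints 37 patients as 21.3%, whereas 37/164 = 22.6%. The difference does not change the result.
- SD of any IADL score by group: not given. The SD ratio r (smaller group / larger group) is therefore **assumed**. No alpha is stated; 95% intervals are assumed.

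**Step 1: coverage of the ordinary interval.** Set the larger group's SD to 1.

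- SE²(ordinary) = [((n1−1)r² + (n2−1)) / (n1+n2−2)] × (1/n1 + 1/n2)
- SE²(true) = r²/n1 + 1/n2
- Coverage = 2Φ(1.96 × SE(ordinary)/SE(true)) − 1

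Example with r = 1.5, n1 = 31, n2 = 114. The pooled variance is (30 × 2.25 + 113)/143 = 1.262. SE(ordinary) = √(1.262 × 0.04103) = 0.228. SE(true) = √(2.25/31 + 1/114) = 0.285. The ratio is 0.80 and coverage is 88%.

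| Assumed r | SE ordinary / SE true | Coverage |
|---|---|---|
| 0.67 | 1.25 | 98.6% |
| 1 | 1.00 | 95% |
| 1.25 | 0.88 | 92% |
| 1.5 | 0.80 | 88% |
| 2 | 0.70 | 83% |

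**Step 2: other splits, same formula**

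- 43 vs 102 (assumed 30% impaired): about 91% at r = 1.5 and 87% at r = 2.
- 72 vs 73 (about half impaired): about 95% at every ratio tried, from 0.67 to 3.
- 17 PDD vs 93 PD-CN (first follow-up counts, taken as a simple pair without the PD-MCI group): about 86% at r = 1.5 and 79% at r = 2.

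**Step 3: do the documents make r > 1 plausible?** Section 7 gives 29.7% converters among patients with baseline cognitive ADL impairment, that is 11 of 37. In total 17 of 164 converted, so 6 of the other 127 did (4.7%). PDD requires impaired ADL function (Section 6.1), so converters should score worse at follow-up.

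Take equal spread within converters and within non-converters, and let converters score d within-class SDs higher (d assumed). Each group's variance is 1 + d²p(1−p), where p(1−p) = 0.297 × 0.703 = 0.209 in the impaired group and 0.047 × 0.953 = 0.045 in the other.

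- d = 2: r = √(1.836/1.180) = 1.25, coverage 92%
- d = 3: r = √(2.880/1.405) = 1.43, coverage 89%
- d = 4: r = √(4.343/1.720) = 1.59, coverage 87%

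This is before covariate adjustment, which may remove part of the difference.

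**Step 4: bounded scores.** Beta-binomial scores on 0–30 were simulated 20,000 times at 31 vs 114, with assumed means.

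| Means, impaired vs other | SD ratio | Ordinary coverage |
|---|---|---|
| 3 vs 3 | 1.0 | 95% |
| 8 vs 5 | 1.19 | 92% |
| 5 vs 2 | 1.5 | 88% |
| 6 vs 1.5 | 1.8 | 84% |

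HC3 intervals covered 93–95% in all these cases. The bounds alone do no harm; unequal spread combined with unequal group size does.

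**The case against.** The strongest objection is that the larger spread is assumed. No IADL mean or SD by group is reported, and Section 7 neither names a standard-error estimator nor mentions confidence intervals for these regressions. With equal SDs the ordinary interval is sound, and with a less variable small group it is conservative. This stands, and it is why the point is conditional.

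Three stronger readings are tempting and are not supported.

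- **That the intervals are too narrow as planned.** Without the SDs this cannot be said.
- **That the larger group sits near zero because 56.7% were cognitively normal at first follow-up.** PD-CN is a cognitive label, not an FAQ score. The FAQ quotient separates cognitive from motor-driven impairment, so patients at or below the cut-off may still have impaired IADL.
- **That the 15 expected converters can be set against everyone else.** Section 7 analyses non-demented vs PDD by logistic regression; its linear contrasts use PD-CN or PD-MCI as reference. The 15 are also additional to the 17 who had already converted.

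Three further limits stand. Section 7 reports that a higher rate of cognitive ADL impairment has since been identified, without a figure, so 31 vs 114 may overstate the imbalance where the newer classification is the predictor. The calculation compares two groups without covariates, whereas the plan adjusts for them. Cognitive status is the primary outcome and its conversion analyses do not use these models.

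None of this answers the omission itself: the plan has an unequal-variance option before adjustment and none after it.

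**Conclusion.** The point holds in conditional form. Section 7 should say how unequal variances are handled in the linear models for IADL outcomes, and it does not. If the smaller group has the larger residual SD, ordinary standard errors at 31 vs 114 would be about 12%, 20% and 30% too small at SD ratios of 1.25, 1.5 and 2 (coverage about 92%, 88% and 83%). That direction is plausible from the scale's floor and the conversion mix, but it is not shown by any reported SD. The loss disappears if SDs are equal or the groups are near even in size. For continuous predictors such as biomarker levels, the direction cannot be determined.

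The reach is limited to the Aim 1.3 linear prediction models and the covariate-adjusted IADL comparisons. The Cox and logistic analyses of conversion and the GLMMs are not affected. Severity is low to moderate.

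**What to change.** Add one sentence to Section 7: linear models with an IADL score as outcome, both the Aim 1.3 prediction models and the covariate-adjusted group comparisons, use heteroscedasticity-consistent (HC3) standard errors for tests and confidence intervals.

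The cost is a software option and somewhat wider intervals. In the simulated cases with unequal SDs, HC3 standard errors were about 11–40% larger than the ordinary ones; with equal SDs they were almost the same and coverage stayed at 93–95%. A proportional-odds model of the FAQ total with the same predictors is an optional check. The first-follow-up FAQ data would show how large the SD ratio is, but the sentence is worth adding whatever they show.
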